#### 9.4.1.2 Progression-free survival

PFS (per RECIST 1.1, as assessed by BICR, will be defined as the time from the date of randomization until the date of objective disease progression or death (by any cause in the absence of progression) regardless of whether the patient withdraws from therapy or receives another anticancer therapy prior to progression (ie, date of event or censoring – date of randomization + 1). Patients who have not progressed or died at the time of analysis will be censored at the time of the latest date of assessment from their last evaluable RECIST 1.1 assessment. However, if the patient progresses or dies after 2 or more missed visits, the patient will be censored at the time of the latest evaluable RECIST 1.1 assessment prior to the 2 missed visits (NE is not considered a missed visit). If the patient has no evaluable visits or does not have baseline data, they will be censored at Day 1 unless they die within 2 visits of baseline, then they will be treated as an event with date of death as the event date.

The PFS time will always be derived from scan/assessment dates and not visit dates.

RECIST 1.1 assessments/scans contributing toward a particular visit may be performed on different dates. The following rules will be applied:

- For BICR assessments, the date of progression will be determined based on the earliest scan dates of the component that triggered the progression for the adjudicated reviewer selecting PD or of the reviewer who read baseline first if there is no adjudication.
- For Investigator assessments, the date of progression will be determined by the earliest of the RECIST assessment/scan dates of the component that indicates progression.
- When censoring a patient for PFS, the patient will be censored at the latest of the scan dates contributing to a particular overall visit assessment.

A sensitivity analysis of PFS will be performed using Investigator assessments according to RECIST 1.1.

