# 9.5.1.1 Progression-free survival

The primary PFS analysis will be based on the programmatically derived RECIST 1.1 using BICR tumor assessments. The analysis will be performed in the FAS using a stratified log-rank test adjusting for TNM stage (I/II versus III) and receipt of PCI (yes versus no). The effect of durvalumab monotherapy and durvalumab and tremelimumab combination therapy versus placebo treatment will be estimated by the hazard ratio (HR) together with its corresponding confidence interval (CI) (95% and [1-adjusted alpha] × 100%) from a stratified Cox proportional hazards model.

In order to ensure there are at least 5 events within each strata; if there are too few events in the Stage I/II stratification level, TNM stage may be excluded from the models leaving receipt of PCI as the sole stratification factor.

Secondary PFS analyses will be performed using the same methodology as for the primary analysis.

Kaplan-Meier plots of PFS will be presented by treatment group. Summaries of the number and percentage of patients experiencing a PFS event and the type of event (RECIST 1.1 or death) will be provided along with median PFS for each treatment group.

Sensitivity analyses will be performed to assess possible evaluation-time bias that may be introduced if scans are not performed at the protocol-scheduled time points. The midpoint between the time of progression and the previous evaluable RECIST assessment will be analyzed using a log-rank test. For patients whose death was treated as PFS event, the date of death will be used to derive the PFS time used in the analysis. This approach has been shown to be robust even in highly asymmetric assessment schedules (Sun and Chen 2010).

Attrition bias will be assessed by repeating the PFS analysis except that the actual PFS event times, rather than the censored times, of patients who progressed or died in the absence of progression immediately following 2 or more non-evaluable tumor assessments will be included. In addition, patients who take subsequent therapy prior to progression or death will be censored at their last evaluable assessment prior to taking the subsequent therapy. This analysis will be

supported by a Kaplan-Meier plot of the time to censoring where the censoring indicator of the PFS analysis is reversed.

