3.2.1 Progression-free survival (PFS)

PFS (per RECIST 1.1 as assessed by the BICR) will be defined as the time from the date of randomization until the date of objective disease progression or death (by any cause in the absence of progression) regardless of whether the patient withdraws from randomized therapy or receives another anti-cancer therapy prior to progression (i.e. date of event or censoring – date of randomization + 1). Patients who have not progressed or died at the time of analysis will be censored at the time of the latest date of assessment from their last RECIST 1.1 assessment. However, if the patient progresses or dies after 2 or more consecutive missed visits, the patient will be censored at the time of the latest RECIST 1.1 assessment prior to the 2 missed visits (Note: NE is not considered a missed visit). A 'look-back' approach will be taken (i.e. if an event e.g. progression or death is observed, then it will be considered an event only if there is an assessment within the 2 visit window immediately before the event, irrespective of whether there were missed visits prior to that assessment). If the patient has no evaluable visits or does not have baseline data they will be censored at Day 1 unless they die within 2 visits of baseline i.e. ≤ 119 days (2 x 8 weeks plus 1 week allowing for a late assessment within the visit window), then they will be treated as an event with date of death as the event date.

Given the scheduled visit assessment scheme (i.e. $q8w \pm 1w$ for the first 72 weeks then $q12w \pm 1w$ up to 96 weeks then $q24w \pm 1w$ thereafter) the definition of 2 missed visits will change. See Appendix B for further details on the derivation of the 2 missed visit rule for RECIST assessments.

The PFS time will always be derived based on scan/assessment dates not visit dates.

PFS will also be obtained using the algorithm described above for the RECIST site investigator tumor data.

RECIST 1.1 assessments/scans contributing towards a particular visit may be performed on different dates. The following rules will be applied:

- For BICR assessments, the date of progression will be determined based on the earliest scan dates of the component that triggered the progression for the adjudicated reviewer selecting PD or of the reviewer who read baseline first if there is no adjudication.

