A sensitivity analysis will be performed to assess possible evaluation-time bias that may be introduced if scans are not performed at the protocol-scheduled time points. The midpoint between the time of progression and the previous evaluable RECIST assessment (using the final date of the assessment) will be analyzed using a stratified log-rank test, as described for the primary analysis of PFS. Note that midpoint values resulting in non-integer values should be rounded down. For patients whose death was treated as a PFS event, the date of death will be used to derive the PFS time used in the analysis. This approach has been shown to be robust to even highly asymmetric assessment schedules (Sun and Chen 2010). To support this analysis, the mean of patient-level average inter-assessment times will be tabulated for each treatment group. This approach will use the BICR RECIST assessments.

Attrition bias

Attrition bias will be assessed by repeating the primary PFS analysis except that the actual PFS event times, rather than the censored times, of patients who progressed or died in the

absence of progression immediately following two, or more, non-evaluable tumor assessments will be included. In addition, patients who take subsequent therapy (note radiotherapy is not considered a subsequent anti-cancer therapy) prior to their last RECIST assessment or progression or death will be censored at their last assessment prior to taking the subsequent therapy. This analysis will be supported by a Kaplan-Meier plot of the time to censoring from the primary analysis where the censoring indicator of the PFS analysis is reversed. This approach will use the BICR RECIST assessments.

• Ascertainment bias

Ascertainment bias will be assessed by analyzing the site investigator data. The stratified log rank test will be repeated on the programmatically derived PFS using the site investigator data based upon RECIST. The HR and CI will be presented.

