APPENDIX B. 2 MISSED VISIT RULES

RECIST 1.1. Assessments

For RECIST 1.1 assessments, we will apply a 'look-back' approach to the 2 missed visit rule. That is, if an event (e.g. progression or death) is observed, then it will be considered an event only if there is an assessment within the 2 visit window immediately before the event, irrespective of whether there were missed visits prior to that assessment. If there are 2 consecutive missed visits prior to the event, the event will be censored as the last valid RECIST 1.1 assessment, prior to the 2 missed visits. For example:

Week 8	Week 16	Week 24	Week 32	Week 40	Censor for 2 missed visit rule?
Event?	Event?	Event?	Event?	Event?	_
No	Missed visit	Missed visit	No	Yes	No
No	No	Missed visit	Missed visit	Yes	Yes – censor at week 16

Given the scheduled visit assessment for RECIST (i.e. $q8w \pm 1w$ for the first 72 weeks then $q12w \pm 1w$ up to 96 weeks then $q24w \pm 1w$ thereafter) the definition of 2 missed visits window will change:

Length of 2 missed visit window for RECIST assessments

Missing baseline or within 2 visits of baseline:

- A patient without baseline will be censored at day 1 unless they die ≤ day 119 (week 17).
- Any scan ≤ day 119 (week 17) is within 2 visits of baseline and therefore cannot be censored for missing visits.

Schedule: q8w:

 For any scan > day 119 until ≤ day 511 (week 73) the visit schedule is q8w ±1 week and thus the maximum time between two consecutive scans is 1+8+8+1=18 weeks (126 days).

Schedule: change from q8w to q12w:

 For any scan > day 511 until ≤ day 595 (week 85) the visit schedule is q12w ±1 week and the visit schedule for the cycle before was q8w ±1 week and thus the maximum time between two consecutive scans is 1+8+12+1=22 weeks (154 days).

Schedule: q12w:

 For any scan > day 595 until ≤ day 679 (week 97) the visit schedule is q12w ±1 week and the visit schedule for the cycle before was q12w ±1 week thus the maximum time between two consecutive scans is 1+12+12+1=26 weeks (182 days).

[figure not shown]
Schedule: change from q12w to q24w:

[figure not shown]
 For any scan > day 679 until ≤ day 847 (week 121) the visit schedule is q24w ±1 week and the visit schedule for the cycle before was q12w ±1 week and thus the maximum time between two consecutive scans is 1+12+24+1=38 weeks (266 days).

[figure not shown]
Schedule: q24w:

[figure not shown]

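### The PFS attrition-bias analysis restores events after non-evaluable scans, but the primary rule censors events after missed visits, so as worded the missed-visit-censored events stay censored

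*SAP*

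**What the plan says.** **Primary rule.** Under SAP 3.2.1, a patient who progresses or dies after at least two missed visits in a row is censored at the latest RECIST assessment "prior to the 2 missed visits (Note: NE is not considered a missed visit"). Appendix B applies this as a look-back: "If there are 2 consecutive missed visits prior to the event, the event will be censored as the last valid RECIST 1.1 assessment". Protocol 9.4.1.2 has the same rule, censoring at the "latest evaluable RECIST 1.1 assessment prior to the 2 missed visits (NE is not considered a missed visit"). A second rule in SAP 3.2.1 covers patients with nothing to evaluate: "If the patient has no evaluable visits or does not have baseline data they will be censored at Day 1", with an exception for death by day 119.

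**Attrition-bias analysis.** SAP 4.2.2 repeats the primary analysis but uses "the actual PFS event times, rather than the censored times, of patients who progressed or died in the", and the sentence continues "absence of progression immediately following two, or more, non-evaluable tumor assessments will be included". It also censors patients at their last assessment before subsequent therapy. Protocol 9.5.1.1 has the same trigger: "patients who progressed or died in the absence of progression immediately following 2 or more non-evaluable tumor assessments will be included". SAP Table 7 lists this analysis under alternative censoring rules.

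**Terms.** In SAP 3.1 and 3.1.1, NE is the visit response given to a tumor assessment that took place but could not be read. The supportive summaries in SAP 4.2.2 count patients who miss assessments as a separate item.

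**The concern.** A sensitivity analysis for attrition should undo the censoring that attrition caused. Here the censoring follows missed visits, while the restoration is triggered by scans that were done and read as NE. A programmer who applies the SAP's own definition of NE would leave every ordinary missed-visit-censored progression or death censored.

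PFS by BICR is a dual primary endpoint, and SAP 4.2.2 puts the primary and sensitivity hazard ratios together on a forest plot. If the attrition HR agrees with the primary HR, readers may conclude that missed-visit censoring did no harm, although that was never tested.

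**Working it through.** **1. The plan's own example.** Appendix B shows a patient assessed at week 16 who misses weeks 24 and 32 and has an event at week 40. The gap is 40 − 16 = 24 weeks = 168 days. The two-visit window on the 8-weekly schedule is 1 + 8 + 8 + 1 = 18 weeks = 126 days. Since 168 > 126, the event is censored at week 16, as the SAP states. Now suppose weeks 24 and 32 were scanned and read as NE. NE is not a missed visit, so the last assessment is week 32, the gap is 8 weeks = 56 days, and the event counts. The first patient is the one to restore; the second needs no restoring.

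**2. Both rules applied to visit patterns** (E = evaluable, no progression; N = NE; M = missed):

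| Visits before the event | Event | Primary analysis | Attrition analysis as worded |
|---|---|---|---|
| E-E-M-M | progression or death | censored | still censored |
| E-E-N-N | progression or death | event | unchanged |
| E-E-M-N, E-E-N-M, E-M-M-E | progression | event | unchanged |
| N-N-N | death after day 119 | censored at Day 1 | restored |

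The clause changes only the last row, which is censored by the Day 1 rule and not by the missed-visit rule. The documents do not say how follow-up scans in a patient without baseline data are classed, so a few of those patients might also be reached.

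**3. Other planned PFS analyses.**
- Evaluation-time bias moves progression dates to midpoints and restores nothing.
- Ascertainment bias keeps the same censoring: "PFS will also be obtained using the algorithm described above for the RECIST site investigator tumor data".
- The conditional imputation under ascertainment bias concerns site progressions without central confirmation.
- Deviation bias is optional and excludes patients.
- By-arm counts of missed assessments and premature censoring, and the reverse Kaplan-Meier plot, are descriptive. TFST and OS are different endpoints. None gives a PFS HR with the events restored.

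**4. Design reference (SAP 1.3, 5.1).** At 370 events and the final level of 0.444%, z = 2.845. Critical HR = exp(−2 × 2.845/√370) = 0.744, against 0.743 stated. Power at HR 0.65 = Φ(√370 × |ln 0.65|/2 − 2.845) = Φ(4.143 − 2.845) = 90.3%, against about 90% stated.

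**5. Possible size.** Inputs from the documents: 262 per arm, medians 10 and 15.4 months (HR 0.65), 38 months' accrual, cut-off at 370 events, no missed-visit censoring up to day 119. Assumed: exponential PFS, uniform accrual, affected events censored 18 to 26 weeks early, unstratified Cox model, and the affected shares. There were 2,000 replicates per scenario. Entries are mean HR censored → restored; recomputing a percentage from the rounded HRs can differ by about 0.1 point.

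| Affected, durvalumab / placebo | Share of events | Share of patients |
|---|---|---|
| 1% / 1% | 0.653 → 0.653 (+0.1%) | 0.648 → 0.650 (+0.3%) |
| 3% / 3% | 0.656 → 0.657 (+0.1%) | 0.648 → 0.653 (+0.8%) |
| 5% / 5% | 0.651 → 0.652 (+0.2%) | 0.645 → 0.653 (+1.3%) |
| 5% / 1% | 0.635 → 0.655 (+3.1%) | 0.618 → 0.650 (+5.3%) |
| 1% / 5% | 0.671 → 0.652 (−2.8%) | 0.678 → 0.654 (−3.5%) |

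About 4 to 19 events are affected in the first column and 5 to 26 in the second. The 18-to-26-week gap simplifies Appendix B, whose window grows to 38 weeks after day 679 and 50 weeks after day 847. With the Appendix B windows, the unequal event-share cases give about +3.1% and −2.5%. Applying the shares only to events after day 119 gives +2.2% and −1.7%.

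**The case against.** The intent is fairly clear. The text contrasts actual event times with censored times, and under SAP 3.2.1 only the missed-visit rule and the Day 1 rule censor an observed event, so the clause has real content only if it targets those. The SAP is also not strict about the word: a patient with no evaluable visits, or who dies with no evaluable assessments, naturally includes one whose visits were all missed. On this view the defect is a slip of terminology. The effect is small when the arms are alike, and a 5% against 1% imbalance is an invention in a double-blind trial with one scan schedule. The planned by-arm counts would show such an imbalance.

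Much of this stands. Missed visits were probably meant, the effect is probably small, and an imbalance would be visible. It does not make the stated trigger right. Two or more non-evaluable assessments most naturally means assessments that took place, and both documents say that NE is not a missed visit. The counts can signal that a re-analysis is needed, but they do not supply it. One rare sequence (two NE scans, then two missed visits, then an event) could be restored on some readings of the clause; the ordinary case could not.

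**Conclusion.** The concern holds as a matter of wording. Followed literally, the attrition-bias analysis leaves the missed-visit-censored events censored, reaches at most some patients censored at Day 1, and otherwise largely reduces to censoring at subsequent therapy. No planned analysis re-estimates the PFS HR with those events restored.

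The primary test, its alpha and its power do not change. The shift that a corrected analysis would show cannot be computed from the documents. Under the assumed shares it is 1.3% or less when the arms are alike and lies between −3.5% and +5.3% at 5% against 1%; no mean HR crosses 0.743. It is material only if missed visits differ between arms, which is what this analysis should examine. The correction should be made, but it does not threaten the primary conclusion.

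**What to change.** In SAP 4.2.2, change the trigger to: *2 or more consecutive missed visits (as defined in Appendix B) or non-evaluable tumor assessments*. This restores every event that the missed-visit rule censors. Record the change in SAP Section 6, or make the same edit in protocol 9.5.1.1. It would help to add whether events in patients censored at Day 1 are also restored.

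The cost is one phrase, one line in Section 6 (or one protocol phrase), and one sensitivity analysis programmed to the corrected trigger. No new data are needed.

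A minor separate point: protocol 9.4.1.2 censors at the last evaluable assessment, SAP 3.2.1 drops the word evaluable, and Appendix B refers to the last valid assessment. SAP Section 6 does not list this difference. Restore the word in SAP 3.2.1 or list the change.

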If there is an important discrepancy between the primary analysis using the BICR assessments and this sensitivity analysis using investigator assessments, then the proportion of patients with site but no central confirmation of progression will be summarized; such patients have the potential to introduce bias in the central review due to informative censoring. An approach that imputes an event at the next visit in the central review analysis may help inform the most likely HR value (Fleischer et al 2011), but only if an important discrepancy exists.

Disagreements between investigator and central reviews of RECIST progression will be presented for each treatment group. The summary will include the early discrepancy rate which is the frequency of central review declared progressions before the investigator review as a proportion of all central review progressions and the late discrepancy rate which is the frequency of central review declared progressions after the investigator review as a proportion of all discrepancies.

Deviation bias

Deviation bias may be assessed by repeating the PFS analysis excluding patients with deviations that may affect the efficacy of trial therapy (see Section 2.2).

A forest plot illustrating the hazard ratio and 95% confidence interval will be provided for each treatment comparison to compare the primary and sensitivity analyses of progression-free survival.

Duration of follow-up

Duration of follow-up will be summarized using medians (as well as minimum and maximum):

- Time from randomization to the date of PFS event for patients who experience PFS events or to the date of censoring summarized in all patients regardless of treatment arm, as well as by treatment arm;
- Time from randomization to the date of censoring in censored patients only, presented by treatment arm

Subgroup analyses

Subgroup analyses will be conducted comparing PFS (per RECIST 1.1 using BICR assessments) between durvalumab monotherapy and durvalumab and tremelimumab combination therapy versus placebo in the following subgroups of the FAS and combination analysis set respectively (but not limited to):

- TNM stage (Stage I/II, III) based on both IVRS and eCRF data
- Receipt of PCI (yes, no) based on both IVRS and eCRF data
- Time from end date of cCRT to randomization in this study (<14 days (2 weeks), ≥14 to <28 days (4 weeks), ≥28 days)

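### The late discrepancy rate in SAP 4.2.2 leaves investigator-only progressions out of its numerator, so with other counts equal it falls as they become more frequent

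*SAP*

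**What the plan says.** The text is the ascertainment-bias part of SAP 4.2.2, which has three elements.

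- **Lead analysis, unconditional.** "Ascertainment bias will be assessed by analyzing the site investigator data": the stratified log-rank test is repeated on investigator-assessed PFS, with a hazard ratio and CI.
- **Conditional follow-up.** The SAP commits that "the proportion of patients with site but no central confirmation of progression will be summarized", but attaches a condition to this: "If there is an important discrepancy between the primary analysis using the BICR assessments and this sensitivity analysis using investigator assessments". The reason given for the summary is that "such patients have the potential to introduce bias in the central review due to informative censoring". The SAP adds, under the same condition: "An approach that imputes an event at the next visit in the central review analysis may help inform the most likely HR value". It gives no criterion for when a discrepancy counts as important.
- **Disagreement table, unconditional and by arm.** Two rates must appear in it. One is a "late discrepancy rate which is the frequency of central review declared progressions after the investigator review as a proportion of all discrepancies". Its companion is an "early discrepancy rate which is the frequency of central review declared progressions before the investigator review as a proportion of all central review progressions".

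The section does not define the set of all discrepancies. It also does not say how a progression called by only one of the two assessments enters either rate.

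**The concern.** Investigator-only progressions are the disagreements most relevant to bias in a central-review endpoint, and other parts of the SAP show how they could arise. Management follows the investigator's RECIST assessment (SAP 3.1.1). Imaging runs to RECIST progression plus one follow-up scan (SAP 3.1). A patient with neither central progression nor death is censored at the last RECIST assessment (SAP 3.2.1). An investigator call that central review does not share can therefore end the central record early, for a reason related to prognosis.

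A by-arm table of disagreements is where a reader would look for this. If its late rate misses these patients, or falls as they increase, it gives false comfort about one of the two primary endpoints.

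**Working it through.** **Inputs.** The two definitions come from SAP 4.2.2. Neither document gives a value or threshold for either rate, or any discrepancy counts, so there is no stated figure to reproduce and every count below is an assumption.

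**Cells, per arm.** a1 = both call progression, same date; a2 = both, central earlier; a3 = both, central later; b = investigator only; c = central only.

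**Rates as worded.**
- Late = a3 / (a2 + a3 + b + c). Cell b has no central progression, so it is outside the numerator. It is a disagreement, so on the plain reading it is in the denominator.
- Early = a2 / (a1 + a2 + a3 + c). Cell c is in the denominator but has no investigator date to precede.

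**Direction.** Write D = a2 + a3 + b + c. Adding one patient to b changes the late rate from a3/D to a3/(D + 1), a fall whenever a3 > 0. When a3 = 0 the rate stays at zero.

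**Two illustrative arms.** a1 = 110, a2 = 20, a3 = 20 and c = 20 in both; b = 15 in one and 35 in the other.
- Late, as worded: 20/(20+20+15+20) = 20/75 = 26.7%, and 20/(20+20+35+20) = 20/95 = 21.1%. The arm with more than twice as many unconfirmed investigator progressions looks 5.6 points better.
- Late, with b in the numerator: (20+15)/75 = 46.7%, and (20+35)/95 = 57.9%. The same arm is now 11.2 points worse.
- Early, as worded: 20/(110+20+20+20) = 20/170 = 11.8%. With c in the numerator: 40/170 = 23.5%.

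**Range over b**, with a2 = 20, a3 = 20, c = 10:
- As worded: b = 0, 20/50 = 40.0%; b = 10, 20/60 = 33.3%; b = 30, 20/80 = 25.0%; b = 60, 20/110 = 18.2%.
- With b counted as late: 20/50 = 40.0%; 30/60 = 50.0%; 50/80 = 62.5%; 80/110 = 72.7%.

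Over a grid of a2 from 0 to 60, a3 from 5 to 60 and c from 0 to 40, raising b from 10 to 30 lowered the rate as worded in every case, by 0.6 to 26.7 points.

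**Alternative reading.** If all discrepancies meant timing differences only, the late rate would be a3/(a2 + a3). With a2 = a3 = 20 it is 20/40 = 50% whatever b is. If investigator-only cases replace late central calls (a3 = 10, b = 10), it drops to 10/30 = 33.3%. This reading also misses the group.

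**When other cells differ.** If the arm with b = 35 also has a3 = 35, with a2 = c = 20, the rate as worded is 35/(20+35+35+20) = 35/110 = 31.8%, above the 26.7% of the arm with b = 15. The fall with b is therefore a statement with the other cells held fixed.

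**The case against.** The strongest reply is that this rate carries little weight.

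- It is one descriptive line, with no threshold, test or decision attached. The lead ascertainment check is the investigator-PFS log-rank test and hazard ratio, where an investigator-only progression can count as an event, and a forest plot sets it beside the primary result. This stands.
- The disagreement table must include the two rates but is not limited to them. SAP 4.2.2 also summarizes premature censoring by arm, days from censoring to data cut-off, and a Kaplan-Meier plot of time to censoring. These would pick up some of the patients. This stands in part, because none of those summaries identifies an investigator progression as the reason.
- The set of all discrepancies is undefined, so the downward movement depends on the plain reading. This also stands in part: on the timing-only reading the fault is omission, not a fall with each added case.

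Two stronger inferences are tempting and unsupported. A reader might infer that the table always favours the arm with more investigator-only progressions; the 31.8% example shows that it need not. A reader might also equate more such patients with more informative censoring. Under SAP 3.2.1, death without central progression is still a BICR PFS event unless it follows two or more consecutive missed visits, and the follow-up scan may still show central progression. Some of these patients will therefore have a BICR event.

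**Conclusion.** The definition needs correcting, as a fault in a supporting summary. Investigator-only progressions cannot enter the late-rate numerator. On the plain reading, with other cells equal and at least one late central call, each added case lowers the rate. The size depends on counts that the documents do not give: a gap of 5.6 points in one direction becomes 11.2 points in the other in the illustration. Central-only progressions have a related but weaker problem in the early rate, since one could arguably be read as preceding an investigator call that never came.

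The only planned statistic that explicitly counts the investigator-only group depends on a condition with no stated criterion, so it may not be produced. A reader might go further and conclude that the ascertainment assessment as a whole, or the BICR PFS result, is compromised. The documents do not support that: the investigator-PFS analysis is unconditional, and no primary test, alpha or power calculation uses these rates.

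**What to change.** In SAP 4.2.2:

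1. Define all discrepancies as a2 + a3 + b + c, in words.
2. Define the late rate as (central progression after the investigator's + investigator progression with no central progression) / all discrepancies.
3. Define the early rate as (central progression before the investigator's + central progression with no investigator progression) / all central progressions.
4. Report the number and proportion of investigator-only progressions by arm at every PFS analysis, without the condition on the two analyses differing.

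The next-visit imputation can stay conditional. The cost is a few sentences of SAP wording and a small change to one table program, with no new data.
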